10. For details of light breakfast and light snack composition, refer to Section [4.1.4](#).
11. If ketamine infusion is interrupted for a technical reason, the reason to be eliminated as soon as possible, before start of a new test, after the ongoing test has been completed (if applicable). An interruption of maximum of 15 min for technical reasons is allowed. For details, refer to Section [4.1.2](#).
12. Ketamine infusion can be prolonged for a maximum of 15 min, i.e. to 105 min in total, in case delays from the planned time occur for CANTAB tests, [REDACTED]; or terminated earlier, if the above assessments on ketamine are completed (or any test drops out) [REDACTED]
13. Confirmation of recovery from ketamine must be confirmed via criteria of recovery from ketamine after a minimum of 60 min of recovery follow up. For details, refer to Section [5.2.5.6](#).
14. Vital signs at 5 min prior to start of ketamine infusion include recording of respiratory rate and effort, and will serve as baseline for confirmation of recovery from ketamine. For details, refer to Section [5.2.5.6](#)
15. If several actions are indicated at the same time point, the intake of meal will be the last action.
16. Discharge after assessment of fitness by the investigator or designee.
17. **Drug administration (1) at planned time 0:00:** BI 425809 or Placebo to BI 425809. For details, refer to Section [4.1.4](#).
18. **Drug administration (2) at planned time 3:00:** BI 409306 + Placebo to Lamotrigine, or Lamotrigine + Placebo to BI 409306, or Placebo to BI 409306 + Placebo to Lamotrigine. For details, refer to Section [4.1.4](#).
19. The selected tests from the **CANTAB test battery** will be done with a 4 min break in between each test in the following sequence: **Rapid Visual Information Processing (RVP)**, **Spatial Working Memory (SWM)**, **Paired Associates Learning (PAL)**. For details, refer to Section [5.4.1](#).

24. For details of vital signs evaluation, refer to Section [5.2.2](#), [Flow Chart C](#) and [Flow Chart D](#).
25. From start of ketamine infusion until confirmation of recovery from ketamine, oxygen saturation (SaO₂) will be monitored continuously. For other details of vital signs recording, refer to [Flow Chart C](#) and [Flow Chart D](#).
26. For details of safety laboratory evaluation, refer to Section [5.2.3](#).

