	13:03	[REDACTED] Questioning for AEs ¹ Vital Signs (BP, PR, SaO ₂) ¹	¹ [REDACTED], right before CANTAB RVP
5:06	13:06	CANTAB RVP	
	13:13	[REDACTED] Vital Signs (BP, PR, SaO ₂) ¹	[REDACTED], right before CANTAB SWM
	13:17	CANTAB SWM	
	13:23	[REDACTED] Vital Signs (BP, PR, SaO ₂) ¹	[REDACTED], right before CANTAB PAL
	13:27	CANTAB PAL	
	13:39	Questioning for AEs Vital Signs (BP, PR, SaO ₂)	
5:40	13:40	[REDACTED]	
	13:53	Vital Signs (BP, PR, SaO ₂)	
	13:54	[REDACTED]	
	13:57	[REDACTED]	
	14:00	Vital Signs (BP, PR, SaO ₂)	
	14:01	[REDACTED]	
	14:12	Vital Signs (BP, PR, SaO ₂)	
	14:13	[REDACTED]	
	14:19	Questioning for AEs Vital Signs (BP, PR, SaO ₂)	
6:20	14:20	[REDACTED]	
6:30 ¹	14:30 ¹	Vital signs (BP, PR, SaO ₂) [REDACTED] Stop of ketamine infusion¹ Stop of continuous ECG and SaO ₂ monitoring	¹ can be prolonged for a maximum of 15 min, in case delays from PT occur for CANTAB, [REDACTED] [REDACTED] or terminated earlier, if the above tests are completed (or any test drops out)
6:45	14:45	Vital Signs (BP, PR, SaO ₂)	
7:00	15:00	Questioning for AEs Vital Signs (BP, PR, SaO ₂) 12-lead ECG	
7:15	15:15	Vital Signs (BP, PR, SaO ₂)	
7:30 ¹	15:30 ¹	Questioning for AEs Vital Signs (BP, PR, SaO ₂) Confirmation of recovery from ketamine^{2,3} 240 mL fluid intake	¹ a minimum of 60 min of recovery follow up ² as per criteria of recovery from ketamine ³ lunch will be served after confirmation of recovery
8:00	16:00	[REDACTED]	
9:00	17:00	[REDACTED]	

Proprietary confidential information © 2021 Boehringer Ingelheim International GmbH or one or more of its affiliated companies

10:00	18:00	Questioning for AEs Vital Signs (BP, PR) 12-lead ECG	dinner will be served in the evening
24:00 ¹	08:00 ¹	Questioning for AEs Vital Signs 12-lead ECG Safety Laboratory (blood, urine) ^{2,3}	¹ Day 2 at V3, V4 and V5. The time is approximate; the procedures to be performed and completed \pm 2 h. ² Hematology, Biochemistry, Coagulation, Urinalysis ³ breakfast will be served after blood sampling
27:00 ¹	11:00 ¹	Questioning for AEs Vital Signs C-SSRS 'since last visit' DSST, MOAA/S, CADSS, SFST Targeted Physical Examination ² Discharge from trial site³	¹ time is approximate; the procedures to be performed and completed within 2 h prior to discharge ² incl. skin inspection for signs of rash, check for lymphadenopathy and neurological examination ³ after confirmation of fitness by the investigator, and at least 24h after the last study drug administration

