- The initial intravenous ketamine bolus has to be administered over a period of 60 seconds as more rapid administration may result in respiratory depression or apnoea and enhanced pressor response
- Close monitoring of blood pressure, pulse rate and oxygen saturation during and after ketamine infusion

Proprietary confidential information © 2021 Boehringer Ingelheim International GmbH or one or more of its affiliated companies

- Continuous ECG monitoring during and after ketamine infusion until confirmation of recovery from ketamine
- Recovery from the ketamine administration will be followed up for at least 60 min after stop of infusion, until confirmation of recovery from ketamine as per criteria of recovery from ketamine, and must be documented. (see Section [5.2.5.6](#)).

- Visual acuity test will be performed at the Screening Examination and the End of Trial Examination, and also in case visual disturbances develop. Subjects with ophthalmologic disorders will be excluded from the study.
- Regular safety laboratory examinations, including haematology to monitor for blood dyscrasias
- Only healthy subjects with no co-medication will be enrolled.
- In case AEs occur that require treatment, anti-epileptic drugs (AEDs) are not allowed
- Prior to discharge the subjects will be assessed by an investigator for their fitness, including a DSST, MOAA/S, CADSS and a SFST, and suicidality including C-SSRS. Their in-house refinement can be extended anytime if deemed necessary by the medical judgment of the investigator
- Subjects will be informed that driving an automobile, operating hazardous machinery or engaging in hazardous activities should not be undertaken for 24 hours or more after ketamine infusion

Drug-induced liver disease

Although rare, a potential for drug-induced liver injury (DILI) is under constant surveillance by sponsors and regulators. Therefore, this trial requires timely detection, evaluation, and follow-up of laboratory alterations in selected liver laboratory parameters to ensure subjects' safety; see also Section [5.2.6.1.4](#), adverse events of special interest.

Summary

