4.2 OTHER TREATMENTS, EMERGENCY PROCEDURES, RESTRICTIONS

4.2.1 Other treatments and emergency procedures

No specific rescue medication is foreseen for BI 409306 and BI 425809, and there are no special emergency procedures to be followed. No additional treatment is planned. However,

Proprietary confidential information © 2021 Boehringer Ingelheim International GmbH or one or more of its affiliated companies

if adverse events require treatment, the investigator can authorise symptomatic therapy. In those cases, subjects will be treated as necessary and, if required, kept under supervision at the trial site or transferred to a hospital until all results of medical evaluations are acceptable.

In case of ketamine overdose, respiratory depression can occur requiring supportive ventilation. Each time after start of ketamine infusion until confirmation of recovery from ketamine, oxygen saturation (SaO₂) will be monitored continuously, and if SaO₂ is <90%, a prompt medical evaluation is to be done. Mechanical support of respiration that will maintain adequate blood oxygen saturation and carbon dioxide elimination is preferred to administration of analeptics.

- In case of clinically significant changes in blood pressure and pulse rate during the ketamine infusion, the infusion has to be stopped immediately. Treatment, e.g. with α₂-agonists (e.g. Clonidine) or β-blockers may be initiated in case of sustained and severe hypertension and tachycardia [[P19-11590](#)].
- If the subject experiences distressing psychomimetic symptoms, the ketamine infusion has to be stopped and further treatment with benzodiazepines, such as midazolam or diazepam may be indicated [[P19-11590](#)].
- If the subject experiences distressing psychomimetic symptoms, the ketamine infusion has to be stopped and further treatment with benzodiazepines, such as midazolam or diazepam may be indicated [[P19-11590](#)].
- In the rare event of ketamine-induced seizures, treatment should be started with benzodiazepines followed by barbiturates or propofol if persistent [[P19-11590](#)].

Following a suspected lamotrigine overdose, hospitalization and general supportive care is indicated, including frequent monitoring of vital signs and close observation of the patient. Induction of emesis should be considered. It is uncertain whether haemodialysis is an effective means of removing lamotrigine from the blood.

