5.2.2 Vital signs

Systolic and diastolic blood pressures (BP) as well as pulse rate (PR) will be measured by a blood pressure monitor (e.g. Dinamap Pro 100, [REDACTED] or comparable) at the times indicated in the [Flow Chart](#), after subjects have rested for at least 5 min in a supine position when possible.

Pulse oximetry is a non-invasive method for monitoring O₂ saturation (SaO₂). A blood-oxygen monitor displays the percentage of blood that is loaded with oxygen and used to

Proprietary confidential information © 2021 Boehringer Ingelheim International GmbH or one or more of its affiliated companies

detect abnormalities in ventilation. SaO_2 will be measured by a pulse oximeter (e.g. [REDACTED]
[REDACTED] TruSat, [REDACTED] or comparable).

All recordings should be made using the same type of blood pressure and oxygen saturation recording instrument on the same arm, if possible.

At the screening examination (Visit 1), orthostatic tests will be performed. Subjects should have spent at least 5 min in the supine position before blood pressure and pulse rate will be measured the first time. Further 2 measurements will be performed immediately after standing up and after 3 min in a standing position.

At the screening ketamine challenge (Visit 2) and on treatment days (Visits 3, 4 and 5):

- Before ketamine infusion and after confirmation of recovery from ketamine, vital signs (BP, PR, SaO_2) to be measured at the time points indicated in the [Flow Chart C](#) and [Flow Chart D](#). Vital signs 5 min prior to start of ketamine infusion (incl. recording of respiratory rate and effort this time) will serve as baseline for confirmation of recovery from ketamine.*
- During ketamine infusion, vital signs (BP, PR, SaO_2) to be measured and recorded in the breaks between the tests at the time points indicated in the [Flow Chart C](#) and [Flow Chart D](#). Oxygen saturation (SaO_2) will be monitored continuously from start of ketamine infusion until confirmation of recovery from ketamine (see below). If SaO_2 is <90%, a prompt medical evaluation is to be done.*

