- After stop of the ketamine infusion, vital signs to be measured every 15 minutes for at least 60 min until confirmation of recovery from ketamine. Recovery must be confirmed via criteria of recovery from ketamine as compared to pre-ketamine infusion. Vital signs 5 min prior to start of ketamine infusion (incl. recording of respiratory rate and effort this time) will serve as baseline. Recovery follow up can be terminated after a minimum of 60 minutes when all applicable recovery criteria are met (see Section [5.2.5.6](#)).*

Blood pressure and pulse rate values will be collected in the CRF. Oxygen saturation, respiratory rate and effort assessments will be kept in source data only, but not collected in the CRF. Only clinically relevant abnormal findings will be reported as AEs.

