5.2.4 Electrocardiography

5.2.4.1 12-lead ECG

Twelve-lead ECGs (I, II, III, aVR, aVL, aVF, V1 - V6) will be recorded using a computerised electrocardiograph (e.g. CardioSoft EKG System, [REDACTED] [REDACTED] or comparable) at the times provided in the [Flow Chart](#).

To achieve a stable heart rate at rest and to assure high quality recordings, the site personnel will be instructed to assure a relaxed and quiet environment, so that all subjects are at complete rest.

All ECGs will be recorded for a 10 sec duration after subjects have rested for at least 5 min in a supine position when possible. ECG assessment will always precede all other study procedures scheduled for the same time to avoid compromising ECG quality.

All ECGs will be stored electronically. Electrode placement will be performed according to the method of Wilson, Goldberger and Einthoven modified by Mason and Likar (hips and shoulders instead of ankles and wrists).

All locally printed ECGs will be evaluated by the investigator or a designee. Abnormal findings will be reported as AEs (during the trial) or baseline conditions (at screening) if assessed to be clinically relevant by the investigator. Any ECG abnormalities will be carefully monitored and, if necessary, the subject will be removed from the trial and will receive the appropriate medical treatment.

ECGs may be repeated for quality reasons (for instance, due to alternating current artefacts, muscle movements, or electrode dislocation) and the repeated ECG will be used for analysis. Additional (unscheduled) ECGs may be collected by the investigator for safety reasons.

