5.2.4.2 Continuous ECG monitoring

Cardiac rhythm (including heart rate) will be monitored by means of continuous 3-lead ECG recording using e.g. CARESCAPE Monitor B450 (██████████) or comparable from start of ketamine infusion until confirmation of recovery from ketamine. This continuous ECG monitoring supports the early detection of adverse events such as clinically relevant bradycardia, tachycardia, or arrhythmia at the trial site.

Beyond this clinical evaluation at the trial site, no further data collection or analyses are performed based on continuous ECG monitoring.

ECG data from continuous ECG recording will not be transferred to the clinical trial database. Abnormal findings during continuous ECG recording will be recorded as AEs if judged clinically relevant by the Investigator.

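### Flow Charts C and D end continuous ECG and SaO2 monitoring when the ketamine infusion stops, but the text requires both until recovery is confirmed, at least 60 minutes later

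*Protocol*

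**What the plan says.** Flow Charts C and D are the minute-by-minute schedules for the screening challenge and the three treatment challenges. At planned time 6:30 each lists the stop of the infusion and, in the same row, "Stop of continuous ECG and SaO" (the SaO2 subscript and the word monitoring follow). The footnote on that row only lets the infusion be prolonged or ended early; it does not mention monitoring.

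The text sets a later end point.

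- **ECG.** Section 1.4 lists among the risk-minimising measures "Continuous ECG monitoring during and after ketamine infusion until confirmation of recovery from ketamine". Section 5.2.4.2 has the 3-lead recording run "from start of ketamine infusion until confirmation of recovery from ketamine".
- **SaO2.** Flow Chart A footnote 25 begins "From start of ketamine infusion until confirmation of recovery from ketamine, oxygen saturation" and requires continuous monitoring over that interval. Section 4.2.1 ("Each time after start of ketamine infusion until confirmation of recovery from ketamine, oxygen saturation") sets the same duration and asks for prompt medical evaluation below 90%. Section 5.2.2 says that SaO2 "will be monitored continuously from start of ketamine infusion until confirmation of recovery from ketamine".

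Flow Chart A footnote 13 and Sections 5.2.5.6 and 6.1 put confirmation of recovery at least 60 minutes after the infusion stops. Charts C and D plan it at 7:30.

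**The concern.** The two chart rows and the text give different stopping rules for the same monitoring. The charts are what staff work from on the challenge day. A site that follows them drops, for the recovery hour, a safety measure listed in Section 1.4 and the continuous SaO2 rule of Sections 4.2.1 and 5.2.2. The low-risk conclusion of Section 1.4 relies on the implemented safety measures.

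The hour is one in which the protocol itself expects drug to be present: Section 1.2.4.2 gives ketamine a beta-phase half-life of 2.5 hours. Section 1.2.4.3 lists arrhythmias and respiratory depression as uncommon and apnoea as rare. Section 1.4 notes that neither BI compound had been given together with ketamine before.

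One decision rule depends directly on this interval. Discontinuation criterion 7 in Section 3.3.4.1 covers SaO2 below 90% during the infusion and for 30 minutes after it. Without continuous SaO2, its post-infusion part rests on spot readings.

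**Working it through.** The plan has no statistical figure to reproduce here. The check compares the two rules and does the clock arithmetic.

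| Source | Signal | Continuous monitoring ends |
|---|---|---|
| Flow Chart C, 6:30 row | ECG and SaO2 | with the infusion, 6:30 |
| Flow Chart D, 6:30 row | ECG and SaO2 | with the infusion, 6:30 |
| Section 1.4 | ECG | at confirmed recovery |
| Section 5.2.4.2 | ECG | at confirmed recovery |
| Flow Chart A, footnote 25 | SaO2 | at confirmed recovery |
| Section 4.2.1 | SaO2 | at confirmed recovery |
| Section 5.2.2 | SaO2 | at confirmed recovery |

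The five text statements agree with each other; the two chart rows are the outliers.

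**Length of the gap.** The planned stop in the charts is 6:30. The earliest stop under the text is 6:30 + 60 min = 7:30, so the gap is at least 60 min. Continuous monitoring lasts 6:30 − 5:00 = 90 min under the charts and at least 7:30 − 5:00 = 150 min under the text. If the infusion is prolonged by the permitted 15 min, it ends at 6:45 and the text requires monitoring to at least 7:45, which is 165 min.

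**What remains under the charts.** Section 5.2.2 provides that "After stop of the ketamine infusion, vital signs to be measured every 15 minutes for at least 60 min until" recovery is confirmed. After the stop, the charts place these at 6:45, 7:00, 7:15 and 7:30: four readings at 15-minute spacing. A desaturation shorter than 15 minutes can fall between two of them. The 30-minute post-infusion window of criterion 7 runs from 6:30 to 7:00 and contains two of these readings (6:45 and 7:00). For ECG, the hour contains one 12-lead recording, at 7:00; Section 5.2.4.1 says "All ECGs will be recorded for a 10 sec duration".

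**How often it arises.** Each completer has 1 screening + 3 treatment infusions = 4. For 36 completers that is 4 × 36 = 144, plus screening infusions in subjects who are not randomised. This counts exposures to the conflict, not events missed.

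**Precedence.** Footnote 32 of Flow Chart A sends readers to Section 5.2.4 for continuous ECG, and footnote 25 sends them to Charts C and D only for other vital-sign details. Both point towards the text. In the other direction, Section 5.2.1 includes continuous ECG among the items done at the times shown in the Flow Chart, and Section 6.1 tells sites to keep to Charts C and D for vital-sign and ECG times until recovery. No clause settles the conflict.

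**The case against.** The contradiction and the 60 minutes are not in dispute. The case on the other side concerns weight.

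- **The intended reading can be recovered.** For SaO2, footnote 25 and Section 5.2.2 leave the spot schedule to the charts and fix the continuous duration themselves. This largely stands for SaO2. It is weaker for ECG because of the wording of Section 5.2.1. Clear intent makes the correction easy, but it does not cancel an explicit contrary line in the working schedule.
- **Section 6.1 is about discrete time points.** It speaks of planned times and does not name continuous monitoring. That is fair: it is weak support for following the charts on this point, and the finding does not depend on it.
- **Harm is conditional and safeguards remain.** A site would have to follow the chart line against five consistent statements, and nothing shows that any site would. Even then, vital signs are taken every 15 minutes, a 12-lead ECG is done at 7:00, and a physician or qualified care provider must stay available until the Section 5.2.5.6 criteria are met, including saturation above 94% on room air. All of this stands and limits the severity.
- **No analysis is touched.** Continuous ECG data do not enter the database and SaO2 stays in source data; only clinically relevant findings reach the analysis, as adverse events. This is correct.

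**Conclusion.** The concern holds. Flow Charts C and D are wrong as written at 6:30: they end continuous ECG and SaO2 monitoring at least 60 minutes before the text allows, at every ketamine infusion. The consequence is limited to safety surveillance in the recovery hour, chiefly the post-infusion part of criterion 7, where a brief desaturation could be missed. The primary endpoint is measured earlier and is unaffected.

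This rests on the current text of both places, on the planned times in the charts, and on reading the text as the intended rule. The documents give no rate from which a difference in detection could be derived, and none is claimed. The correction should be made, but it is not critical to the trial's conclusions.

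**What to change.** In Flow Charts C and D, delete the entry that stops continuous ECG and SaO2 monitoring from the 6:30 row and place it in the 7:30 row, at the confirmation of recovery. Word it as an event: monitoring stops when recovery is confirmed, not earlier than 60 minutes after the infusion stops. That wording also covers infusions that are prolonged or ended early. Leave Flow Chart A footnote 25 and Sections 1.4, 4.2.1, 5.2.2 and 5.2.4.2 as they are.

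The edit is one line in each of two charts and adds no procedure beyond what the text already requires. The real cost is administrative: Global Amendment 2, which also changed Charts C and D, was marked for implementation only after approval by the IRB, IEC or competent authority, and the same step may apply here.

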C-SSRS	Columbia Suicidal Severity Rating scale
CTL	Clinical Trial Leader
CTM	Clinical Trial Manager
CTP	Clinical trial protocol
CTR	Clinical trial report
DDI	Drug drug interaction
DILI	Drug induced liver injury
DRESS	Drug reaction with eosinophilia and systemic symptoms
DSST	Digit Symbol Substitution Test
[REDACTED]	[REDACTED]
ECG	Electrocardiography

Proprietary confidential information © 2021 Boehringer Ingelheim International GmbH or one or more of its affiliated companies

eCRF	Electronic case report form
EDC	Electronic data capture
EDTA	Ethylenediaminetetraacetic acid
[REDACTED]	[REDACTED]
[REDACTED]	[REDACTED]
EoT	End of trial
ERP	Event-Related Potential
ET	Eye tracking
FEP	First episode of psychosis
FU	Follow-up
GCP	Good Clinical Practice
GlyT1	Glycine transporter 1
HLH	Hemophagocytic Lymphohistiocytosis
HR	Heart rate
HV	Hyperventilation
IB	Investigator's brochure
IEC	Independent Ethics Committee
IPD	Important protocol deviation
IQRMP	Integrated Quality and Risk Management Plan
IRB	Institutional Review Board
ISF	Investigator site file
i.v.	Intravenous
LC-MS/MS	Liquid chromatography with tandem mass spectrometry
LTP	Long term potentiation
MOAA/S	Modified Observer's Assessment of Alertness/Sedation
MDA	Methylenedioxymethamphetamine
MDMA	Methylenedioxymethamphetamine
MedDRA	Medical Dictionary for Regulatory Activities
MMN	Mismatch-Negativity
NMDA	N-methyl-D-aspartate
NMDAR	N-methyl-D-aspartate receptor
PAL	Paired Associates Learning
PCR	Polymerase chain reaction
PD	Pharmacodynamic(s)
PDE9	Phosphodiesterase-9
P-gp	P-glycoprotein
[REDACTED]	[REDACTED]
PM	Poor metaboliser

Proprietary confidential information © 2021 Boehringer Ingelheim International GmbH or one or more of its affiliated companies

PR	Pulse rate
qd	Quaque die, once daily
██████████	██████████
qPCR	Quantitative polymerase chain reaction
QT	Time between start of the Q-wave and the end of the T-wave in an electrocardiogram
QTc	QT interval corrected for heart rate using the method of Fridericia (QTcF) or Bazett (QTcB)
R	Reference treatment
REP	Residual effect period
R _{max}	Maximum rate of urinary excretion
RVP	Rapid Visual Information Processing
SAE	Serious adverse event
SaO ₂	Oxygen saturation
SCR	Screening
SD	Standard deviation
SFST	Standardized Field Sobriety Test
SOA	Stimulus onset asynchrony
SOP	Standard operating procedure
SPL	Sound pressure level
SRD	Single-rising dose
ss	(at) steady state
SUSAR	Suspected unexpected serious adverse reaction
SWM	Spatial Working Memory
T	Test product or treatment
TMF	Trial master file
██████████	██████████
██████████	██████████
██████████	██████████
TSAP	Trial statistical analysis plan
WHO	World Health Organization
XTC	Ecstasy

